5.5. Types of report/verification forms

Booklet-type report forms will be used for this investigation.

Report/verification forms to be used in this investigation include "Report Forms for Newly-enrolled Subjects (Booklet 01)," "Follow-up Report Form (Booklet 02 and thereafter)," and "Height Follow-up Form."

5.5.1. Report Forms for Newly-enrolled Subjects (Booklet 01)

Ver.2

"Report Forms for Newly-enrolled Subjects (Booklet 01)" will be used for collecting the data during the assessment year in which the subject is enrolled.

5.5.2. Follow-up Report Form (Booklet 02 and thereafter)

"Follow-up Report Form (Booklet 02 and thereafter)" will be used for collecting the data during the fiscal year following the assessment year in which the subject is enrolled, and each subsequent year thereafter; provided that "Follow-up Report Form (Booklet 02 and thereafter)" will be used from the year of enrollment for patients transferring from "Genotropin Special Investigation - Investigation of Genotropin long-term use in patients with SGA dwarfism without epiphyseal closure."

5.5.3. Height Follow-up Form

"Height Follow-up Form" will be used to collect data concerning body height in patients completing or discontinuing Genotropin therapy, and meeting the following criteria.

- Patients not switching to other drug product
- Patients not reaching adult height (final height)

5.6. Notes concerning completion, correction, and reviewing of report/verification forms

(1) Completion procedures

Investigator will, upon confirming the survey items, complete the report/verification forms with data based on medical record including laboratory data; a pen, ballpoint pen, or other inerasable means should be used to complete the forms. The data after the completion of Genotropin therapy may be collected through telephone or other verbal means.

(2) Data correction

Any corrections on the report to be made by the investigator will be struck out with a double line so that the original description can be legible, and put on a "correction seal". Upon receiving Sponsor's inquiry on the content of report form, the investigator will review the medical record described earlier, and as required, correct relevant sections and resubmit the forms.

(3) Data verification

Upon completion of all entries and corrections in the report/verification forms, the investigator will once again review the information on the forms and associated query forms, and sign or seal/name the relevant sections on the forms.

(4) Submission of report forms

Investigators must prepare a report/verification form and submit it to Sponsor promptly upon the completion of the assessment period and height follow-up period.

Ver.2

6. Assessment variables and time points

Investigator will conduct this investigation in accordance with the following assessment schedule. After the contract is concluded, the investigator shall enroll patients who meet the eligibility criteria, and complete the report/verification form upon confirming the baseline patient characteristics and other relevant data. The data will be collected from the birth of the subject to the completion of investigation (which will be determined by the subject, his/her parent [or a legally acceptable representative], or the attending doctor).

[Assessment schedule]

	Enrollment Form for New Subject	Newly-enrolled subjects Report forms (Booklet 01)	Enrollment Form for Ongoing Subject	Report forms (Booklet 02) Follow up	Height Follow-up Form*
Assessment variables and time points	Enrollment	Assessment period	Enrollment	Assessment period	Height follow-up period
		From commencement of treatment to the fiscal end of the enrollment year		Until the end of the fiscal year**	From completion/discontinuation of treatment to each fiscal end
Patient identification	Identification number	●	●(Copy)	●	●
	Patient's initials (not essential)	●	●(Copy)	●	●
	Gender	●	●(Copy)	●	●
	Date of birth	●	●(Copy)	●	●
	Informed consent	●	●(Copy)	●	
	The date Genotropin therapy is commenced	●	●(Copy)	●	
	The date the initial growth hormone therapy was commenced	●	●(Copy)	●	
	Enrollment eligibility	●	●(Copy)		
Patient characteristics and family history	Height of parents		●		
	Mother's birth history		●		
	Presence/absence of family history of GHD		●		
	Twin/multiplets		●		
	Childbirth procedures		●		
	Fetus week number		●		
	Apgar score		●		
	Birth height		●		
	Birth weight		●		
	Birth head circumference		●		
	Body height at 1 year prior to the commencement of treatment		●		
	GH tolerance test		●		
	Clinical history		●		
	Past treatment history		●		
	Pregnancy status (Only for women)		●		●
Dose record of Genotropin		●		●	
Concomitant therapy		●		●	
Examinations/tests		●		●	●***
Patient's profile		●		●	
Adverse events		●		●	

●: Variables to be recorded

*: The data after the completion of Genotropin therapy may be collected through telephone or other verbal means.

** : For the initial fiscal assessment period of patients transferring from "Genotropin Special Investigation - Investigation of Genotropin long-term use in patients with SGA (small-for-gestational age) dwarfism without epiphyseal closure," a "Follow-up Report Form (Booklet 02 and thereafter)" will be completed with data collected during a period starting on the day following the final assessment of data recorded in the last booklet of the previous investigation and ending with the fiscal end of the applicable year.

***: Height, weight, pubescence, and bone age

Ver.2

6.1. Patient identification

The following information should be recorded in the enrollment, report, and verification forms:

- [1] Identification number
- [2] Patient's initials (not essential)
- [3] Gender
- [4] Date of birth
- [5] Informed consent
- [6] The date Genotropin therapy is commenced
- [7] The date the initial growth hormone therapy was commenced
- [8] Enrollment eligibility

6.2. Family history and patient characteristics

(1) The following information obtained at the commencement of Genotropin therapy will be recorded:

- [1] Height of parents (to the first decimal place)
- [2] Mother's birth history (the first childbirth / multipara)
- [3] Presence/absence of GHD family history
- [4] Twin/multiplets
- [5] Childbirth procedures
- [6] Fetus week number
- [7] Apgar score
- [8] Birth height (to the first decimal place)
- [9] Birth weight (to the first decimal place)
- [10] Birth head circumference (to the first decimal place)
- [11] Body height at 1 year prior to the commencement of treatment (to the first decimal place), and the date of measurement
- [12] GH tolerance test
- [13] Clinical history (past history and concurrent disease)
 - Silver-Russell syndrome
 - Name(s) of disease/syndrome
 - Past or current regarding the following clinical history
Chronic disease (including allergy), disease requiring medical treatment, disease/disorder accompanied by surgery, hospitalization, and/or subsequent complications, or any other

Ver.2

disease/syndrome determined problematic; of which, those occurred prior to the commencement of Genotropin therapy will be considered as "Past history", and those concurrent at the commencement of Genotropin therapy will be considered as "Concurrent disease".

[14] Prior medications

Presence/absence of growth hormone therapy intended for the treatment of SGA (small-for-gestational age) dwarfism without epiphyseal closure used until the day before the commencement of Genotropin therapy

(2) The following status will be recorded until the completion of assessment period for each booklet:

[1] Presence/absence of pregnancy, and the actual or expected date of birth [women only]

[2] Verification of revisits since the commencement of treatment (this checkmark is not required if not applicable)

6.3 Dose record of Genotropin

The following information concerning dose record of Genotropin will be recorded until the completion of assessment period for each booklet:

[1] Weekly dosage

[2] Dose frequency per week

[3] Preparation/dosage form

[4] Duration of treatment

[5] Reason for change

6.4 Concomitant therapies

(1) Concomitant medications

The following information concerning all concomitant medications used will be recorded until the completion of assessment period for each booklet. Information concerning drugs temporally associated with adverse events should also be collected, including all drugs used in such patients between the commencement of Genotropin therapy and the onset of each such adverse event, as well as drugs used for the treatment of the adverse event.

[1] Name of drug (brand name)

[2] Route of administration

[3] Duration of treatment

[4] Reason for treatment

(2) Non-drug therapy

The following information concerning non-drug concomitant therapies used will be recorded until the

Ver.2

completion of assessment period for each booklet. Information concerning non-drug therapies temporally associated with adverse events should also be collected, including all non-drug therapies used in such patients between the commencement of Genotropin therapy and the onset of each such adverse event, as well as non-drug therapies used for the treatment of the adverse event.

- [1] Name of therapy
- [2] Duration of treatment
- [3] Reason for treatment

6.5. Examinations/tests (clinical laboratory/clinical course)

Results of the following parameters tested will be recorded until the completion of assessment period for each booklet; provided that Booklet 01 should include the results prior to the commencement of Genotropin therapy. Of the results of examinations and tests performed prior to the commencement of Genotropin therapy, those within 1 month prior to the commencement of Genotropin therapy should be recorded (including the date the Genotropin therapy is commenced).

- [1] Carbohydrate metabolism related tests (fasting or continuous glucose, HbA1c), serum lipid concentration (total cholesterol, triglyceride), thyroid function related tests (TSH, free T4), and IGF-I
- [2] Height (to the first decimal place), weight (to the first decimal place), and head circumference (to the first decimal place)
- [3] Pubescence
- [4] Bone age
- [5] Body composition

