7. HANDLING OF MISSING VALUES

Any missing data on the seriousness, measures taken, and outcome of adverse events will be handled as “unknown” in summarizing data.

Measured values outside the acceptable range (Appendix 1) at each evaluation time point of the efficacy endpoints and clinical laboratory parameters will be handled as missing and missing data will not be imputed.

The procedure to handle uncleaned data is described below.

- Items with missing data: Missing data will be handled as missing (“unknown” for the category of classification variables) for both tabulation and listing.
- Items with inconsistent data: Inconsistent data will be handled as missing for both tabulation and listing. In this regard, however, a data handling list will be prepared separately.
- No signature: Descriptions in the report form without signature of the contract physician (or with signatures of other physicians than the contract physician) will be handled as missing for both tabulation and listing. No date or inconsistent date in the signature date section (eg, date of signature before or after the start date of treatment) will be considered to indicate that there is no signature on the report form.

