8.2.4.2. Change in Height SDS

The summary statistics of measured values of height SDS at each age will be calculated for the efficacy analysis set and eligible criteria set. The evaluation points are according to [Appendix A1.1](#) Definition of timing for visit 1. The change in height SDS will be plotted with a solid line for individual male and female patients separately, with age on the horizontal axis and height SDS on the vertical axis. The start of treatment will be indicated as ▲, pubescence as ●, and reaching adult height (near final height) as ▼. They will be plotted with a dotted line after the completion/discontinuation of treatment.

The same calculation will be performed to prepare plots in the same manner for the set of patients who reached adult height (near final height) and set of patients not reached.

The summary statistics of measured values of height SDS at each evaluation point and change from the start of Genotropin will be calculated for a set of patients who reached adult height (near final height). The 95% confidence interval of the mean of the change will be calculated. The evaluation points are according to [Appendix A1.2](#) Definition of timing for visit 2. The change in height SDS will be plotted with a solid line for individual male and female patients separately, with evaluation points on the horizontal axis and height SDS on the vertical axis. The start of treatment will be indicated as ▲, pubescence as ●, and reaching adult height (near final height) as ▼. They will be plotted with a dotted line after the completion/discontinuation of treatment.

The summary statistics of measured values of height SDS at each evaluation point and changes from the start of Genotropin will be calculated in the efficacy analysis set and eligible criteria set. The 95% confidence interval of the mean of the change will be calculated. The evaluation points are according to [Appendix A1.3](#) Definition of timing for visit 3. The change in height SDS will be plotted with a solid line for individual male and female patients separately, with evaluation points on the horizontal axis and height SDS on the vertical axis. The start of treatment will be indicated as ▲, pubescence as ●, and reaching adult height (near final height) as ▼. They will be plotted with a dotted line after the completion/discontinuation of treatment.

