11. APPENDIXES

11.1. Appendix 1: Details of Data Extraction

A1.1 DEFINITION OF TIMING FOR VISIT 1

Timing for visit	Endpoint	Definition [allowable range]
3 years	Height Height SDS Body weight SDS BMI SDS IGF-I SDS	3 years and 0 month to 3 years and 11 months
4 years	Height Height SDS Body weight SDS BMI SDS IGF-I SDS	4 years and 0 month to 4 years and 11 months
N years	Height Height SDS Body weight SDS BMI SDS IGF-I SDS	N years and 0 month to N years and 11 months

The measured value on the latest date will be used when the same patient receives more than one measurement during the same visit.

A1.2 DEFINITION OF TIMING FOR VISIT 2

Timing for visit	Endpoint	Definition [allowable range]
Start of Genotropin therapy	Height SDS Body weight SDS BMI SDS IGF-I SDS	90 days before the first date of treatment (the start date of treatment) to the start date of treatment for this investigation
Pubescence	Height SDS Body weight SDS BMI SDS IGF-I SDS	The date evaluated as the pubescence +90 days
At reaching adult height (near final height)	Height SDS Body weight SDS BMI SDS IGF-I SDS	The date evaluated to reach adult height (near final height) +90 days

The measured value on the earliest date will be used when the same patient receives more than one measurement during the same visit.

In this regard, all the data measured after reaching adult height (near final height) will be used if plots are prepared.

A1.3 DEFINITION OF TIMING FOR VISIT 3

Timing for visit	Endpoint	Definition [allowable range]
Start of Genotropin therapy	Laboratory test parameters Height SDS Height velocity Height velocity SDS Body weight SDS BMI SDS IGF-I SDS	90 days before the first date of treatment (the start date of treatment) to the start date of treatment for this investigation
1 year later	Laboratory test parameters Height SDS Height velocity Height velocity SDS Body weight SDS BMI SDS IGF-I SDS	365 ±90 days after the start of treatment
2 years later	Laboratory test parameters Height SDS Height velocity Height velocity SDS Body weight SDS BMI SDS IGF-I SDS	730 ±90 days after the start of treatment
N years later	Laboratory test parameters Height SDS Height velocity Height velocity SDS Body weight SDS BMI SDS IGF-I SDS	365 × N ±90 days after the start of treatment
Completion of Genotropin therapy	Laboratory test parameters Height SDS Height velocity Height velocity SDS Body weight SDS BMI SDS IGF-I SDS	Final date of treatment for this investigation (completion date of treatment) ±90 days

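### For newly enrolled children the protocol records pre-treatment results from 1 month back, but the SAP accepts a baseline from 90 days back, so some usable baselines are never collected

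*Protocol*

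**What the plan says.** **Collection.** Protocol section 6.5 covers laboratory tests (HbA1c and IGF-I among them), height, weight, head circumference, pubescence, bone age and body composition. It asks for results during each booklet's period, "provided that Booklet 01 should include the results prior to the commencement of Genotropin therapy". It then limits how far back to go: "those within 1 month prior to the commencement of Genotropin therapy should be recorded", with the start date itself included. Protocol 5.5.1 and 5.5.2 assign Booklet 01 to newly enrolled children. Children transferring from the previous investigation use Booklet 02 onward.

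**Analysis.** SAP Appendix 1 defines the start-of-treatment visit in both A1.2 and A1.3 as "90 days before the first date of treatment (the start date of treatment) to the start date of treatment for this investigation". If several values fall in a window, "The measured value on the earliest date will be used when the same patient receives more than one measurement during the same visit". Under SAP section 7, a value outside the allowable range "will be handled as missing and missing data will not be imputed".

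**Use of the baseline.** For height SDS, SAP 8.2.4.2 states that "changes from the start of Genotropin will be calculated in the efficacy analysis set and eligible criteria set", with a 95% confidence interval for the mean change. Similar change summaries are planned for HbA1c (8.2.3.3), height velocity and its SDS (8.2.4.3, 8.2.4.4), body weight SDS (8.2.4.5), BMI SDS (8.2.4.6) and IGF-I SDS (8.2.4.7).

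Neither document mentions or explains the difference between the two windows.

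**The concern.** The analysis is prepared to use a baseline up to 90 days old, but the collection rule does not ask sites for anything older than about a month. A child whose only pre-treatment HbA1c was taken, for example, two months before the first dose has a value in the chart that the SAP would accept and that the protocol does not request.

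This is an observational database. The protocol schedules no baseline test of its own, and forms are completed from existing medical records (Protocol 5.6). Enrolment can follow the start of treatment, with the assessment period traced back (Protocol 5.3.1, 5.4.1), so a missing baseline test cannot be done later.

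What is at stake is the number of children in the change-from-start tables, variable by variable, and hence the precision of those estimates. HbA1c deserves attention because it is the only laboratory parameter for which SAP 8.2.3.3 specifies a change summary.

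**Working it through.** The plan has no figure of its own to reproduce. The target of 400 comes without a derivation, and neither document estimates baseline availability.

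**Inputs from the documents**
- Collection window: 1 month before start, start date included (Protocol 6.5). A month is 28 to 31 days.
- Acceptance window: day -90 to the start date (SAP A1.2, A1.3).
- Missing baseline: no imputation (SAP section 7).
- Target: 400 children (Protocol section 3), not split into new and ongoing.

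**Inputs assumed, because the documents do not give them**
- q, the share of newly enrolled children whose last value of a given variable lies in the gap: 5% to 30%.
- s, the share of the 400 who are newly enrolled: 100%, 50% or 25%.

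**Step 1: compare the windows.** Day -90 to day 0 is 91 days. The 1-month rule covers 28 + 1 = 29 to 31 + 1 = 32 of them, or 32% to 35%. The remaining 91 - 32 = 59 to 91 - 29 = 62 days (65% to 68%) have no requested data. With a 30-day month the gap is days -90 to -31. These are shares of days in the window, not shares of children.

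**Step 2: follow one child.** A newly enrolled child has a last IGF-I result in the gap and none later up to the start date. Protocol 6.5 does not ask for it, so no value reaches the A1.3 start visit. With no imputation, change in IGF-I SDS cannot be calculated, and the child is absent from that summary. If the same child's height was measured on the start date, the height SDS change is unaffected. The height recorded for 1 year before start (Protocol 6.2) lies outside the 90-day window and cannot serve as baseline.

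**Step 3: illustrate the size.** Lost baselines per variable = 400 × s × q. Relative confidence interval width = √(400 / (400 - lost)). This takes the standard deviation of change as unchanged, supposes that all 400 would otherwise contribute, and counts no loss among ongoing children.

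| Newly enrolled (s) | q = 5% | q = 10% | q = 20% | q = 30% |
|---|---|---|---|---|
| 100% | 20 lost, ×1.026 | 40 lost, ×1.054 | 80 lost, ×1.118 | 120 lost, ×1.195 |
| 50% | 10 lost, ×1.013 | 20 lost, ×1.026 | 40 lost, ×1.054 | 60 lost, ×1.085 |
| 25% | 5 lost, ×1.006 | 10 lost, ×1.013 | 20 lost, ×1.026 | 30 lost, ×1.040 |

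For example, √(400 / 280) = 1.195.

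**Step 4: compare the two ways of aligning the texts.** Extending collection to day -90 lets all 91 days supply a baseline. Narrowing the SAP to 1 month makes the documents agree but recovers no child.

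**Step 5: check the selection rule.** If a child has values on day -90 and day 0 and both are recorded, A1.2 and A1.3 take day -90. Collecting older values without changing that rule would replace some close baselines with distant ones.

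**The case against.** The strongest reply is that the windows are nested, not contradictory. The 90-day range contains the 1-month range, so the SAP discards nothing collected under Protocol 6.5. Appendix 1 labels its windows as allowable ranges, and a tight collection rule with a wider tolerance is coherent. A recent value is also arguably the better baseline in a growing child, because an older height adds pre-treatment growth to the apparent change. All of this stands. It rules out calling the documents inconsistent, but it does not help the child whose only value is in the gap.

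A reader might infer several stronger claims that the documents do not support:

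- **That all children are exposed.** The 1-month rule is tied to Booklet 01. SAP 2.1 brings in ongoing children's data from the previous investigation, whose pre-treatment window is not given. A loss of 40-120 of 400 would need every child to be newly enrolled and an assumed 10-30% in the gap; nothing supports a 10% floor, and the true share could be near zero.
- **That an affected child leaves every change analysis.** Missingness is by variable, and the by-age summaries under A1.1 need no baseline.
- **That height is as exposed as the laboratory values.** Enrolment requires a current height and a pre-treatment height velocity (Protocol section 2), and the starting dose is expressed per kg body weight (SAP 8.2.2). A height or weight close to the start is therefore likely.
- **That the loss is selective towards sites that test less often.** This is plausible, but no testing frequencies are given.
- **That older values are barred or gone.** Protocol 6.5 says what should be recorded and does not forbid more. The charts may still hold the values.

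The stakes are also modest. SAP section 4 makes all testing exploratory with no decision rule, and the patient counts required by SAP 8.1.1 will show any shortfall.

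**Conclusion.** The point holds in a limited form. For newly enrolled children, a variable last measured on about days -90 to -31 has no requested baseline, although the SAP would accept one, and the child is lost from that variable's change-from-start summary. HbA1c and IGF-I are the most plausible cases; height SDS, and with it the main growth results, is less likely to be affected.

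The size cannot be derived from the documents. With 5-30% assumed in the gap, the loss per variable is 20-120 baselines (intervals 3-20% wider) if all 400 are newly enrolled, 10-60 (1-9% wider) if half are, and 5-30 (1-4% wider) if a quarter are. Any effect for ongoing children is unknown.

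This is an inexpensive improvement in data yield. It is not a flaw that undermines the analysis.

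**What to change.** 1. Amend Protocol 6.5 and the Booklet 01 instruction: keep the 1-month request, and add that, when no result for a variable exists within that month or on the start date, the most recent result within 90 days before the start is recorded with its date. This displaces no closer baseline.
2. For newly enrolled children already in the database, retrieve such values through the routine query round. Protocol 5.6 already provides for sponsor inquiries answered from the medical record.
3. In the same edit, have SAP A1.2 and A1.3 use the latest value on or before the start date for the start-of-treatment visit only. The rule for later visits need not change.

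The cost is one added instruction in the protocol and form, one line in the SAP and a small chart-query burden. No new test is needed. The downside is that some baselines will be up to 90 days old, which the SAP already allows.
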